4.1.6 Masking and procedures for unmasking

4.1.6.1 Masking

Part A of the trial is open label. Part B is designed double-masked. The treatments administered (active or sham injection) will be masked to subjects and to the dedicated personnel of the trial site. The table below summarizes the masking level of individual functions in Part B of the trial.

Table 4.1.6.1:1 Overview about masking status of trial role and functions in Part B

Role/function	Timing of Unmasking / receiving access to the treatment information (including rationale)
Subjects	Masked until data ready for final analysis.
Investigator/Site staff	Masked until data ready for final analysis.
Pharmacist*	Unmasked during trial conduct.
Injector**	Unmasked during trial conduct
Sponsor (incl. clinical trial/project team) SMC and database	Unmasked descriptive analyses will be performed on the subjects in the database during the trial conduct (see Section 7.3.7). The release of the treatment information at the individual time points will be documented accordingly.
Bioanalytical Staff	Unmasked as requested for analysis of bioanalytical samples.

* Unmasked independent pharmacist (qualified person) with no other involvement in the trial will prepare the active IVT injection

** Unmasked independent injector with no other involvement in the trial will administer active/sham injections.

Within the central ECG lab, readers involved with interval measurements will be masked with respect to treatment, visit and demographic information collected. During the time a role/function is masked, the treatment information is kept restricted by the global Randomization Team (gRT) per Sponsor Standard Operating Procedure (SOP).

4.1.6.2 Unmasking and breaking the code

Emergency unmasking will be available to the investigator via IRT. It must only be used in an emergency situation when the identity of the trial drug must be known to the investigator in order to provide appropriate medical treatment or otherwise assure safety of trial subjects. The reason for unmasking must be documented in the source documents and/or appropriate CRF page.

Due to the requirements to report Suspected Unexpected Serious Adverse Reactions (SUSARs), it may be necessary for a representative from BI's Pharmacovigilance group to access the randomization code for individual subjects during trial conduct. The access to the code will only be given to authorised Pharmacovigilance representatives for processing in the PV database system and not be shared further.

4.1.7 Packaging, labelling, and re-supply

The investigational medicinal products will be provided by BI or a designated CRO. They will be packaged and labelled in accordance with the principles of Good Manufacturing Practice (GMP). Re-supply to the sites will be managed via an IRT system, which will also monitor expiry dates of supplies available at the sites.

For details of packaging and the description of the label, refer to the ISF.

4.1.8 Storage conditions

Drug supplies will be kept in their original packaging and in a secure limited access storage area according to the recommended storage conditions on the medication label. A temperature log must be maintained for documentation.

If the storage conditions are found to be outside the specified range, the Clinical Research Associate CRA (as provided in the list of contacts) must be contacted immediately.

4.1.9 Drug accountability

The investigator or designee will receive the investigational drugs delivered by the sponsor when the following requirements are fulfilled:

- Approval of the clinical trial protocol by the IRB / EC
- Availability of a signed and dated clinical trial contract between the sponsor and the investigational site,
- Approval/notification of the regulatory authority, e.g. competent authority,
- Availability of the *curriculum vitae* of the Principal Investigator,
- Availability of a signed and dated clinical trial protocol,
- Availability of the proof of a medical license for the Principal Investigator (if applicable)
- Availability of FDA Form 1572 (if applicable).

Investigational drugs are not allowed to be used outside the context of this protocol. They must not be forwarded to other investigators or clinics.

The investigator or designee must maintain records of the product's delivery to the trial site, the inventory at the site, the use by each subject, and the return to the sponsor or warehouse / drug distribution centre or alternative disposal of unused products. If applicable, the sponsor or warehouse / drug distribution centre will maintain records of the disposal.

These records will include dates, quantities, batch / serial numbers, expiry ('use-by') dates, and the unique code numbers (part A) assigned to the investigational medicinal product and trial subjects. The investigator or designee will maintain records that document adequately that the subjects were provided the doses specified by the Clinical Trial Protocol (CTP) and reconcile all investigational medicinal products received from the sponsor. At the time of return to the sponsor and/or appointed CRO, the investigator or designee must verify that all unused or partially used drug supplies have been returned by the clinical trial subject and that no remaining supplies are in the investigator's possession.

4.2 OTHER TREATMENTS, EMERGENCY PROCEDURES, RESTRICTIONS

4.2.1 Other treatments and emergency procedures

There are no special emergency procedures to be followed.

4.2.2 Restrictions

4.2.2.1 Restrictions regarding concomitant treatment

Medications listed under the exclusion criteria (Section [3.3.3](#)) are restricted during the trial.

For the Study eye no other treatment (IVT or otherwise) is allowed during the trial. The fellow eye can be treated with any on-label drug. The Sponsor will not provide fellow eye treatment or compensate for it.

Any intravitreal treatment and use of medications known to be toxic to the retina, lens or optic nerve (e.g. desferoxamine, chloroquine/hydrochloroquine, chlorpromazine, phenothiazines, tamoxifen, nicotinic acid, and ethambutol) are restricted during the trial.

4.2.2.2 Restrictions on diet and lifestyle

None

4.2.2.3 Contraception requirements

WOCBP (for the definition please refer to Section [3.3.2](#)) and men able to father a child must use two medically approved methods of birth control throughout the trial (from Visit 1 until End of Study visit) one barrier method (condom), and one highly effective non-barrier method.

Men (trial subject or partner of a trial subject) must use a condom (regardless of vasectomy) if their sexual partner is a WOCBP.

WOCBP (trial subject or partner of a trial subject) must use a highly effective method of birth control per ICH M3 (R2) throughout the trial (from Visit 1 until EOS visit) that results in a low failure rate of less than 1% per year when used consistently and correctly if their sexual partner is a man able to father a child.

- Combined (estrogen and progestogen containing) hormonal birth control that prevents ovulation (oral, intravaginal, transdermal).
- Progestogen-only hormonal birth control that prevents ovulation (oral, injectable, implantable).
- Intrauterine device (IUD) or intrauterine hormone-releasing system (IUS).
- Bilateral tubal occlusion

Or

Subjects must abstain from male-female sex if this is defined as being in line with the preferred and usual lifestyle of the subject. Periodic abstinence e.g. calendar, ovulation, symptothermal, post-ovulation methods, declaration of abstinence for the duration of exposure to study drug and withdrawal are not acceptable.

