- Next recommended dose by the BLRM = current dose
- At least 12 subjects have been treated in the trial
- At least 6 subjects have been treated at the MFD

Part B of the study will only start if the highest dose is tolerated. Once the last subject in the highest dose cohort of Part A has attended visit 5 (day15) the SMC will meet and evaluate all

DLE data as well as available systemic and ophthalmological safety data. The decision on whether to proceed to Part B will be taken based on the occurrence of DLEs.

Part B:

In Part B, the highest dose will be used (██████). Thirty subjects will be recruited, 2:1 ratio of active treatment versus sham. Subjects dosed in Part A of the trial will not be included.

Subjects will be randomized to receive either active treatment or sham injection.

In Part B, subjects will receive three consecutive doses/sham injections over a 3-month period (██████████). All subjects included in the part B of the trial, will be observed for safety and efficacy for 12 weeks after the last injection.

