3.3.4.1 Discontinuation of trial treatment

An individual subject will discontinue trial treatment if:

1. The subject wants to discontinue trial treatment, without the need to justify the decision.
2. The subject has repeatedly shown to be non-compliant with important trial procedures and, in the opinion of both, the investigator and sponsor representative, is not willing or able to adhere to the trial requirements in the future.
3. The subject needs to take concomitant medication that interferes with the investigational medicinal product or other trial treatment.
4. The subject can no longer receive trial treatment for medical reasons (such as surgery, adverse events, other diseases, or pregnancy). An AE or clinically significant laboratory change or abnormality occurs that the investigator judge to warranting discontinuation of treatment

If new efficacy/safety information becomes available, Boehringer Ingelheim will review the benefit-risk-assessment and, if needed, pause or discontinue the trial treatment for all subjects or take any other appropriate action to guarantee the safety of the trial subjects.

Even if the trial treatment is discontinued (Part B), the subjects remain in the trial and, given their agreement, will undergo the procedures for early treatment discontinuation and follow-up as outlined in the [Flow Chart II](#) and section [6.2.3](#).

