4.2.2.4 Restrictions regarding gamete donation

Gamete donation must not be performed from the time of the first dose of the investigational drug, and for at least 3 months after the last dose of the investigational drug.

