6.2.3 Follow-up period and trial completion

Subjects must continue to be followed according to the visit schedule (unless they withdraw consent for further follow-up) in order to collect data at the end of the planned observation period. Unscheduled visits will be possible at the discretion of the investigator at any time for safety reason. The unscheduled visit may include any assessments considered necessary by the investigator. All unscheduled visits should be described and documented in the medical /source record. The investigator may decide other treatment options during the follow-up period as deemed medically appropriate.

Part A

Visit 8/End of Study:

The Visit 8/EOS will be performed 42 days after Visit 7 (see [Flow Chart I](#)).
The Visit 8/EOS is the final visit and the End of Study eCRF has to be completed.

Part B

Visit 7/End of Study:

The Visit 7/EOS will be performed 28 days after Visit 6 (see [Flow Chart II](#)).
The Visit 7/EOS is the final visit and the End of Study eCRF has to be completed.

Withdrawal of consent

Every effort should be made to keep the subject in the trial and undergoing the procedures and follow up as outlined in the Flow Charts I and II and Section [6.2.3](#).

If a subject is not willing to continue in the trial and wants to withdraw consent prior to the end of the study, Visit 7 (Part A)/ Visit 6 (Part B) should be scheduled as soon as possible, and also Visit 8/EOS(Part A)/ Visit 7/EOS(Part B) should be performed to assess for safety.

The End of Study eCRF has to be filled in even if subject refuses to participate to the above specified visits.

For AE assessment, laboratory tests, recording of ECG and vital signs, and physical examination during the follow-up period, see Section [5.2](#).

Subjects who discontinue treatment before the end of the planned treatment period should undergo the EOS Visit.

All abnormal values (including laboratory parameters) that are assessed as clinically relevant by the investigator will be monitored using the appropriate tests until a return to a medically acceptable level is achieved. (S)AEs persisting after a subject's EOS Visit must be followed until they have resolved, have been sufficiently characterised, or no further information can be obtained.

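### Contraception ends at the End of Study visit with no minimum time after the last dose, while the gamete-donation bar runs at least 3 months from the last dose: a small gap for completers, larger if EOS comes early

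*Protocol*

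**What the plan says.** Protocol section 4.2.2.3 requires two methods of birth control "throughout the trial (from Visit 1 until End of Study visit". It repeats the EOS end point for the highly effective method used by women of childbearing potential. Inclusion criterion 7 (section 3.3.2, both parts) points back to 4.2.2.3 and adds no duration.

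Section 4.2.2.4 uses another anchor. Gamete donation is barred from the first dose and "for at least 3 months after the last dose of the investigational drug".

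The date of EOS depends on how a subject leaves:

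- **Completers.** Section 3.1 says Part B subjects "will be observed for safety and efficacy for 12 weeks after the last injection". Section 6.2.3 sets the regular spacing: "The Visit 7/EOS will be performed 28 days after Visit 6" in Part B and "The Visit 8/EOS will be performed 42 days after Visit 7" in Part A.
- **Treatment stopped early, Part B.** Section 3.3.4.1: "Even if the trial treatment is discontinued (Part B), the subjects remain in the trial", subject to their agreement. Section 6.2.3 adds that they should have an EOS visit and does not say when.
- **Consent withdrawn.** Section 6.2.3: "Visit 7 (Part A)/ Visit 6 (Part B) should be scheduled as soon as possible", and EOS should also be performed. No interval between the two visits is given for this case. The End of Study eCRF "has to be filled in even if subject refuses to participate to the above specified visits", so refusal of EOS is foreseen.

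**The concern.** A safeguard against exposure in pregnancy would normally be timed from the last exposure. Here contraception is timed from a visit, and that visit can move closer to the last dose when a subject leaves early. The donation bar in the next section does not move in that way.

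This is a first-in-human trial, and section 7.3.5 says the residual effect period after intravitreal dosing is not known. Under the written rule an early leaver could be released from contraception weeks before the donation bar ends. A subject who refuses EOS is given no date at all. What is at stake is the safety wording for a few subjects, not an estimate or a test.

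**Working it through.** **Inputs**

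- Part B last dose: Visit 4, Day 57 ±3 (Protocol Table 10.1:3; dosing at Visits 2, 3 and 4 per section 6.2.2).
- Part B EOS: Visit 7, Day 141 ±7 (same table).
- Part A: single dose on Day 1, EOS on Day 99 ±7 (Flow Chart I).
- Regular spacing from penultimate visit to EOS: 28 days (Part B), 42 days (Part A).
- Length of 3 months, which the protocol does not define: 89-92 days in calendar months, or 84 days if it means 12 weeks. Both are carried through as assumptions.
- Windows are taken around the fixed study days.

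**The plan's own figure.** Part B follow-up = 141 − 57 = 84 days = 12 weeks, which agrees with section 3.1.

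**Completers.** Cover = EOS day − last-dose day. Shortfall = length of 3 months − cover, or 0 if negative.

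| Case | Cover (days) | Short of 89-92 | Short of 84 |
|---|---|---|---|
| Part B, nominal | 141 − 57 = 84 | 5-8 | 0 |
| Part B, shortest in window | 134 − 60 = 74 | 15-18 | 10 |
| Part B, longest in window | 148 − 54 = 94 | 0 | 0 |
| Part A, nominal | 99 − 1 = 98 | 0 | 0 |
| Part A, shortest in window | 92 − 1 = 91 | 0-1 | 0 |

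**Part B subjects who stop treatment and stay on schedule.** If the last dose was at Visit 3 (Day 29 ±3), cover is 141 − 29 = 112 days, with a minimum of 134 − 32 = 102. If it was on Day 1, cover is 140 days, with a minimum of 134 − 1 = 133. There is no gap in either case.

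**Consent withdrawn t days after the last dose.** Assume that the penultimate visit takes place that day and that the regular spacing to EOS is kept. The second assumption is not in section 6.2.3.

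- Part B: EOS falls at t + 28, so the gap is (89 to 92) − 28 − t = (61 to 64) − t.
- Part A: EOS falls at t + 42, so the gap is (89 to 92) − 42 − t = (47 to 50) − t.

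| t (days) | Part B gap | Part A gap |
|---|---|---|
| 0 | 61-64 | 47-50 |
| 14 | 47-50 | 33-36 |
| 28 | 33-36 | 19-22 |
| 56 | 5-8 | 0 |

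On the 12-week reading the values at t = 0 are 84 − 28 = 56 days (Part B) and 84 − 42 = 42 days (Part A).

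Other spacings give other answers. If EOS itself were held 14 days after a dose, the gap would be 89 − 14 = 75 to 92 − 14 = 78 days. If EOS stayed on its planned date, the subject would be in the completer's position or better.

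**Scale against the assumed half-life.** Section 4.1.2 assumes an intravitreal half-life of 9.7 days.

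- Completers: 84 / 9.7 = 8.7 half-lives, and 74 / 9.7 = 7.6 at the window extreme.
- Withdrawal on the day of dosing with regular spacing: 28 / 9.7 = 2.9 (Part B) and 42 / 9.7 = 4.3 (Part A).
- Five half-lives are 5 × 9.7 = 48.5 days. Every completer is past that point; such an early leaver is not.

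**The case against.** The case against acting is substantial, and most of it limits how much weight the point can bear.

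- **No rule is broken.** The two sections restrict different acts, and nothing in the documents requires a common end date. A reader might infer that the sections contradict each other. They do not: a subject can comply with both. This stands.
- **The nominal completer gap may be zero.** The protocol uses 3 months loosely. Section 7.1 speaks of the effect after 3 months of treatment, where the matching visit is Week 12, and section 3.1 places doses on Days 1, 29 and 57 within a 3-month period. This stands for the nominal schedule. On the same reading, up to 10 days remain inside the windows.
- **Exposure is small.** Section 1.4.2.1 expects very low systemic exposure, and completers are 7.6 or more assumed half-lives past the last dose. A reader might infer that completers face a reproductive hazard; the documents give no support for that.
- **The largest figures rest on an interval that is not stated.** This is correct. The 61-64 and 47-50 day figures are conditional on the regular spacing and on withdrawal on the day of dosing.
- **A subject who has withdrawn consent is not bound by trial restrictions.** This is also correct, so for that group the change amounts to dated advice.
- **The advice may exist already.** The patient information is not in this copy, and neither is the full mode-of-action and toxicology text that might explain the 3 months.

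These points keep the severity low. They do not supply a post-dose minimum for contraception, which no section of the two documents contains, or an end date when EOS is refused.

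**Conclusion.** The point holds as a low-severity improvement. Contraception and the donation bar have different anchors, and only the donation bar is tied to the last dose.

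For completers the difference is minor. In Part B it is 5-8 days on the nominal days (0 if 3 months means 12 weeks) and at most 15-18 days inside the visit windows (10 on the 12-week reading). In Part A it is at most 1 day. A reader might take the nominal figure as the ceiling for everyone who does not withdraw; the visit windows alone exceed it.

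The gap that matters needs an early EOS. That follows from withdrawal of consent. It could also follow when a subject stops treatment and does not agree to scheduled follow-up, but this is less certain because no timing is given. A reader might infer that every treatment discontinuation shortens cover. Section 3.3.4.1 does not support that: Part B subjects who stay on schedule have at least 102 days. If the regular spacing is kept, the gap after withdrawal on the day of dosing is up to 61-64 days (Part B) or 47-50 days (Part A), and it shrinks day for day with later withdrawal. If EOS is refused, the end point is undefined rather than shortened.

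No endpoint, analysis or sample-size statement is affected.

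**What to change.** In section 4.2.2.3, replace both EOS end points with: *until the EOS visit or 3 months after the last dose of trial medication, whichever is later*. Because 4.2.2.4 uses the same unit, the two rules then agree on either reading of 3 months, and there is an end date even if EOS is refused.

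In section 6.2.3, under withdrawal of consent, add that the investigator tells an early leaver that date as advice. Carry the same wording into the patient information if it is not already there.

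The cost is wording only, with no added visit or procedure. A Part B completer on schedule would use contraception for 0-8 more days, and for up to 18 more inside the windows. Part A completers would add at most 1 day. The 10 sham subjects in Part B would carry the same small burden without drug exposure, because masking rules out a separate rule for them.

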4.2.2.4 Restrictions regarding gamete donation

Gamete donation must not be performed from the time of the first dose of the investigational drug, and for at least 3 months after the last dose of the investigational drug.

4.3 TREATMENT COMPLIANCE

Compliance will be assured by administration of all trial medication in the study centre. This is performed by a qualified physician. In the MD part the unmasked injector with no other involvement in the trial will administer the trial medication.

Subjects who are non-compliant (for instance, who do not appear for scheduled visits or violate trial restrictions) may be removed from the trial and the eCRF will be completed accordingly (for further procedures, please see [Section 3.3.4.1](#)).

5. ASSESSMENTS

5.1 ASSESSMENT OF EFFICACY

For the endpoints, baseline is defined as the value at Visit 2; if not measured at Visit 2 then baseline is the value at Visit 1. All ophthalmologic examinations will be performed on both eyes, as described below.

Centrally collected ophthalmological data (color fundus photography, SD-OCT, OCTA) will be transferred from the Central Reading Center (CRC) to the sponsor's database. The local measurement data (BCVA, Slit lamp, IOP, LLBCVA) will be transferred to the appropriate eCRFs and will remain at the study sites as source documents.

If clinically significant worsening is observed in the assessments of efficacy during the study, it will be reported as AE in the eCRF (please also refer to Section [5.2.7](#)).

SD-OCT/OCT-Angiography

The retinal layers and their thickness can be visualized and measured by SD-OCT. The assessment will be performed by a qualified person, and only specified OCT equipment will be used. OCTA is a non-invasive imaging technique that provides high-resolution volumetric blood flow information without the use of dye. The assessment is also performed by a qualified person, and only specified device(s) will be used.

OCT and OCTA images will be sent to an independent CRC for evaluation. A detailed manual for OCT and OCTA image acquisition and data transmission will be provided.

Visual Acuity measured by ETDRS letter charts

BCVA will be measured using the early treatment diabetic retinopathy study (ETDRS) VA chart. The BCVA score is the number of letters read correctly by the subject. The assessment will be performed by a trained person under specified conditions regarding examination room and equipment.

